## 9.5. Medical history and current medical conditions

### 9.5.1. Coding

Medical history and current medical conditions will be summarised using the current Medical Dictionary for Regulatory Activities MedDRA (MedDRA Version 25.0 or higher) system organ class (SOC) and preferred term classifications. At the end of the trial, all MedDRA codes will be updated with the latest MedDRA version.

### 9.5.2. Medical history and current medical conditions summaries

The relevant medical history and current medical conditions, including allergies or hypersensitivities (except aMN-related) will be summarised by counts and percentages by primary SOC, PT and toxicity grade for each cohort and overall in FAS. The relevant medical history and current medical conditions will be listed for subjects in FAS.

### 9.5.3. aMN-specific medical history and diagnosis

The medical history related to membranous nephropathy will be summarized by cohort and overall including the following summaries

Disease status at screening (newly diagnosed, relapsed or refractory)

Time since initial aMN diagnosis (months) defined as: [Date of screening – Date of initial diagnosis of aMN + 1 day]/30.4375

- If the date of initial diagnosis of aMN is completely missing, the date will not be imputed and the subject will have a missing time since initial aMN diagnosis
- If only the day is missing, then it will be replaced by the first day of the month
- If both the day and month are missing, then it will be replaced by the first day of the year

Proteinuria remission

Number (%) of subjects with a Proteinuria remission during or following previous therapy before starting MOR202 treatment (overall and split by complete vs. partial remission)

Duration of remission during or following previous therapy (months) (overall and split by complete remission vs. partial remission)

Number (%) of subjects with a remission for  $\geq 6$  months vs.  $< 6$  months during or following previous therapy according to the clinical judgement (months) as entered in the eCRF (overall and split by complete vs. partial remission)

Immunofluorescence test results for anti-PLA2R

Number (%) of subjects with positive/negative immunofluorescence test during remission (overall and by remission categories for complete vs. partial remission)

Anti-PLA2R titre

Number (%) of subjects with anti-PLA2R titre of less than 20.0 RU/ml during remission (overall and split by complete vs. partial remission)

The following calculations will be defined:

- Duration of remission to previous therapy (months): [End date of last remission – start date of remission + 1 day]/30.4375
  - If start or end date is completely missing, then duration of response will not be imputed and is missing.
  - If both day and month are missing, the date will not be imputed
  - If only day is missing for the start date, it will be replaced by the first day of the month
  - If only day is missing for end date, it will be replaced by the last day of the month
- If after imputation, the end date of last remission is after the date of screening, the end date of last remission will be replaced by the date of screening
- If after imputation, the duration of remission is < 6 months, and the result of “Duration of remission during or following previous therapy according to the clinical judgement” in the eCRF is ≥ 6 months, the start date will be replaced by [End date – 6 months - 1 day]
- If after imputation, the duration of remission is ≥ 6 months, and the result of “Duration of remission during or following previous therapy according to the clinical judgement” in the eCRF is < 6 months, the start date will be replaced by [End date – 6 months + 1 day]

## 9.6. Study treatment

### 9.6.1. Exposure

#### Duration of exposure to study drug

Exposure to study treatment will be summarized for the FAS population. The duration of exposure will be calculated as follows:

Duration of exposure (days) = [end date of study drug – start date of study drug + 1 day]

#### Cumulative Dose

The MOR202 dose for each infusion can be calculated following the drug handling manual as follows:

$$\begin{aligned} \text{MOR202 infusion dose (mg)} &= \frac{\text{Actual total infusion volume administered (ml)}}{\text{Total volume in the prepared infusion bag (ml)}} \\ &\times \text{Volume of reconstituted drug solution added into the infusion bag (ml)} \\ &\times 65 \left(\frac{\text{mg}}{\text{ml}}\right) \end{aligned}$$

The cumulative dose is defined as the sum of total doses that the subject received from the first study treatment administration until the last study treatment administration.

A summary table with the following information will be presented by cohort and overall on FAS:

- Duration of exposure (months)
- Duration of exposure categorized as follows:

Days of exposure

>0 to <7 days

- 
- >=7 to <14 days
  - >=14 to <21 days
  - >=21 to <30 days
  - >=30 to <60 days
  - >=60 to <90 days
  - >=90 to <120 days
  - >=120 to <183 days
  - >=183 days

In addition, the cumulative exposure duration will be displayed as described above.

- Number (%) of subjects completing each cycle (Cycle 1, 2, 3, 4, 5, and 6)
- Total number of MOR202 infusions per subject (categorized: 1-2 infusions, 3-4 infusions, etc.)
- Cumulative Dose (mg) per subject

Individual study drug administration data will be listed by subject and cohort on FAS, including the information on start and end times of administration, including the study day, infusion volume, and reason(s) for dose interruptions, if applicable.

Listings of the vial numbers for each subjects per administration will be provided.

#### **9.6.2. Dose reduction**

Not applicable.

#### **9.6.3. Dose interruption**

The number (%) of subjects with at least one temporary interruption (during infusion and interruptions due to toxicity) and the associated reasons will be summarized by cohort, cycle and day on FAS.

#### **9.6.4. Permanent treatment discontinuations**

The number (%) of subjects who discontinued MOR202 permanently and the associated reasons will be summarized and listed by cohort, cycle and day on FAS.

#### **9.6.5. Compliance**

Compliance for a MOR202 infusion (based on infusion volumes) will be calculated by dividing the actual MOR202 infusion dose with the planned MOR202 infusion dose and multiplied by 100 (refer to the drug handling manual for the calculation of the planned MOR202 infusion dose).

Overall compliance for MOR202 per subject (based on cumulative infusion volumes) will be calculated by dividing the sum of actual MOR202 infusion doses with the sum of planned MOR202 infusion doses and multiplied by 100.

A subject is non-compliant for each infusion if the MOR202 dose administered is  $\leq 70\%$  or  $> 130\%$  of the planned MOR202 dose. Such non-compliance is recorded in the eCRF. Subjects with overall compliance  $\leq 70\%$  are excluded from the FAS in the Sensitivity Analysis, refer to section 10.10.

Any MOR202 dose missed without medical reason is considered as non-compliance.

The following information will be displayed by cohort and on FAS:

- Number (%) of subjects in the following compliance categories per single infusion:
  - $\leq 70\%$
  - $> 70\% - \leq 130\%$
  - $> 130\%$
- Summary statistics of compliance per infusion visit
- Number (%) of subjects in the following compliance categories for the overall compliance:
  - $\leq 70\%$
  - $> 70\% - \leq 130\%$
  - $> 130\%$
- Summary statistics of the overall compliance

## 9.7. Prior and concomitant medications and non-drug treatments/procedures

### 9.7.1. Coding

Concomitant medications will be recorded and coded using the WHO Drug Dictionary Enhanced and grouped by Anatomical Therapeutic Chemical (ATC) classes; non-drug treatments/procedures will be coded using the MedDRA (MedDRA Version 25.0 or higher). Tabulations with counts and percentages will show the number of medications and non-drug treatments /percentage used in each class / preferred term by cohorts and overall.

### 9.7.2. Definitions

**Pre-medication:** Medication given prior to MOR202 infusion to mitigate potential infusion-related reactions. Pre-medication encompasses antihistamine, antipyretic and glucocorticoids.

**Prior medication/non-drug treatment:** If the treatment start and stop dates are both before the start of study drug, the medication/non-drug treatment will be classified as prior medication/non-drug treatment. Subjects will only be counted once for multiple drug use by preferred drug name.

**Concomitant medication/non-drug treatment:** If the medication start date is on or after start of study drug, the medication will be considered as concomitant medication. If the medication start date is before start date of study treatment but ongoing or with stop date after the start of study treatment, the medication will be considered as concomitant medication. Subjects will only be counted once for multiple drug use by preferred drug name. If the medication start and stop date are incomplete, the following algorithm will apply to exclude the medication from the category concomitant medication. If the start date is missing and

- If stop day is missing but month is complete, medication will only be excluded from concomitant medication if stop month is before month of treatment start.
- If stop day and month are missing but year is complete, medication will only be excluded from concomitant medication if stop year is before year of treatment start.

- If stop date is completely missing, medication will not be excluded.

### 9.7.3. Data presentation

Summary tables (excluding aMN-specific prior therapies) will be presented by cohort and overall for:

- Prior medications
- Concomitant medications
- Prior non-drug treatments/procedures
- Concomitant non-drug treatments/procedures
- Pre-medications

All summaries will be conducted on FAS. Listings will be shown for pre-medication, prior medication/non-drug treatments or procedures and concomitant medication/non-drug treatments or procedures (excluding aMN-specific prior therapies).

### 9.7.4. aMN-specific prior therapies

A summary table will be presented by cohort and overall on FAS for the following aMN-specific therapies:

**Prior medications/non-drug procedures given for aMN** (= medication with indication given as “Primary disease (aMN)” and end date prior or equal to date of screening)

- Number of subjects (%) with at least one prior medication
- Number of subjects (%) with at least one non-drug procedure
- Time since last prior anti-aMN medication/non-drug procedure (months) (see calculation below)

**Prior immunosuppressive medications** (= medication recorded on prior IST eCRF page with latest end date prior or equal to screening)

- Number of subjects (%) treated with no, one, two and more than two immunosuppressive medication categorized and continuous. Different recordings of the same preferred term according to the WHO Drug Dictionary are not counted as separate immunosuppressive medications.
- Duration of last prior IST (months) (see calculation below)

Separate listings will be presented on prior aMN medications/non-drug procedures and immunosuppressive medications. Listings on IST therapy will include information on:

- Medication name
- Number of the particular IST therapy line
- Therapy start date
- Therapy end date
- Route and dosing regimen
- Date and type of the remission during or following the last IST therapy before start of MOR202 treatment

The following calculations are defined:

- Time since last prior anti-aMN medication/non-drug procedure: [Date of screening – End date of last prior anti-aMN medication/non-drug procedure + 1 day]/30.4375  
If the end date of last prior aMN medication/non-drug procedure is completely missing, the date will not be imputed  
If only the day of the end date is missing, then it will be replaced by the day 15 of the month  
If both the day and month, or year are missing, the date will not be imputed  
If after imputation, the end date of last prior anti-aMN medication/non-drug procedure is after the date of screening, the end date will be replaced by the date of screening  
Duration of last prior IST: [End date of last prior IST – Start date of last prior IST + 1 day]/30.4375  
If the end date or the start date is completely missing, the date will not be imputed  
If both the day and month, or year of the start or end date is missing, the date will not be imputed  
If the day of the start date is missing, it will be replaced by the first day of the month  
If the day of the end date is missing, it will be replaced by the last day of the month, or the date of screening, whichever is first

## 10. EFFICACY ANALYSIS

For the primary completion analysis, the analyses will be performed based on the visits during the safety run-in phase and treatment phase.

For the final analysis, the analyses will be performed based on all the visits during the trial.

### 10.1. Analysis of best immunological response rate

The key secondary objective in this trial is to assess the effect of MOR202 on serum anti-PLA2R antibodies in subjects with aMN in terms of best overall immunological response rate (BIRR).

The best overall immunological response (BIR) is defined as achieving any response of IPR, ICR or sICR at any time during the trial but prior to start of prohibited medication or progression based on the definitions in section 7.13.3.

The best overall immunological response rate (BIRR) is defined as the proportion of subjects with a best overall immunological response. The denominator will be the total number of subjects included in the analysis population.

#### Main Analysis

The main analysis will be conducted on FAS. The following information will be presented by cohort and overall:

- Number (%) of subjects achieving a BIR of IPR at any time during the trial
- Number (%) of subjects achieving a BIR of ICR at any time during the trial
- Number (%) of subjects achieving a BIR of sICR at any time during the trial
- BIRR along with the 95% confidence interval (CI, using the Clopper-Pearson exact method)
- Number (%) of subjects with a BIR of PD at any time during the trial
- Number (%) of subjects classified as Non-responder

For each visit available, the number and percentages of subjects in each of the response categories will be tabulated, including missing response evaluations and subjects with a progressive disease. Subjects, who are not classified in either response category or progressive disease will be tabulated as “*Non-Responders*”. Subjects with no post-baseline assessment of response will be included as “*Non-Responders*”.

If a subject achieves several responses, the subject will be tabulated in the highest achieved response category.

No formal hypothesis testing will be conducted.

### Sensitivity Analysis

The main analysis as described above will be conducted using the PPS population.

Listings of individual responses per visit will be generated on FAS.

## 10.2. Analysis of 24 hour urine

24 hour urine will be collected to assess the following parameters:

- Urine protein
- Urine creatinine
- Urine sodium
- CCI [REDACTED]

The following information will be summarized for each 24 hour urine parameter above by cohort and overall on FAS:

Absolute levels by visit

Absolute and percentage change from baseline to each visit until end of study

Listings with individual urine parameter levels will be generated by visit on FAS.

- The following plots will be generated by cohort on FAS for UPCR and Urine creatinine:
  - Spaghetti plots (time vs. parameter value for each subject)
  - Spaghetti plots (time starting from baseline vs. % change from baseline for each subject) – please add dotted reference lines for upper (50%) and lower (-50%) thresholds.
  - Waterfall plot for relative change from baseline at EOT, FUV and EOS – please add study days under the corresponding subject IDs

## 10.3. CCI [REDACTED]

CCI [REDACTED]

CCI

A large black rectangular redaction box covers the majority of the page content. The text "CCI" is visible in the top-left corner of this redacted area.

10.4. CCI

A black rectangular redaction box covers the content of section 10.4. The text "10.4. CCI" is visible in the top-left corner of this redacted area.

CCI

10.5. CCI

A black rectangular redaction box covers the content of section 10.5. The text "10.5. CCI" is visible in the top-left corner of this redacted area.

CCI

CCI [Redacted]

10.6. CCI [Redacted]

CCI [Redacted]

10.7. CCI [Redacted]

CCI [Redacted]

CCI

A large black rectangular redaction box covering the majority of the page content. The text "CCI" is visible in the top-left corner of the redacted area.

10.8.

CCI

A small black rectangular redaction box covering a few lines of text. The text "CCI" is visible in the top-left corner of the redacted area.

CCI

A large black rectangular redaction box covering the majority of the page content. The text "CCI" is visible in the top-left corner of the redacted area.

10.9.

CCI

CCI

### 10.10. Sensitivity analysis

The sensitivity analysis will be performed on the FAS excluding subjects who received  $\leq 70\%$  of the MOR202 doses overall (please see section 9.6.5 for the details) or who received at least one dose of relevant IST therapies at any timepoint of the study in accordance with the visit windows defined in Table 3. The relevant IST therapies will be identified on a case-by-case basis by a medical review of the concomitant medication listing (please refer to section 7.13.6 for the details) and documented in the data review meeting minutes.

**Table 3. Allowed assessment windows.**

Visit	Target day	Analysis Window
1 week	Day 7	Day 2 to Day 10
2 weeks	Day 14	Day 11 to Day 17
3 weeks	Day 21	Day 18 to Day 26
1 month	Day 30	Day 27 to Day 45
2 months	Day 61	Day 46 to Day 75
3 months	Day 92	Day 76 to Day 107
4 months	Day 122	Day 108 to Day 138

6 months	Day 183	Day 139 to Day 229
9 months	Day 274	Day 230 to Day 320
12 months	Day 366	≥ Day 321

The closest value to the target day should be taken into analysis. If there are two values equidistant from the target date, then the latest value will be taken in the analysis. Unscheduled visits are considered in sensitivity analysis.

The sensitivity analyses will be applied to the following endpoints:

Best immunological response rate, section 10.1

**CCI**

Renal Function assessed by eGFR, section 10.4

Serum Albumin Levels, section 10.5

Kinetics of anti-PLA2R titres, section 10.9

## 11. SAFETY ANALYSES

The analysis of safety assessments in this trial will include the evaluation of:

- Adverse Events
- Vital signs
- Physical Examination
- Electrocardiogram
- Laboratory evaluations

### 11.1. Adverse events

#### Adverse Event (AE)

An AE is defined as any untoward medical occurrence in a subject administered a pharmaceutical product and which does not necessarily have to have a causal relationship with this treatment.

An AE can therefore be any unfavourable and unintended sign (including a clinically relevant abnormal laboratory finding), symptom, or disease temporally associated with the use of an IMP, whether or not considered related to that product. For more details, refer to study protocol section 10.8.5.

All AEs will be recorded with information regarding onset, start and end date/time, relationship to study drug, intensity, toxicity grade, action taken with study drug, treatment of event and outcome.

#### Treatment Emergent Adverse Event (TEAE)

TEAEs are defined as any adverse event reported within the following time interval (including the lower and upper limits), which is referred to as the treatment-emergent period:

[Start date of study drug, End date of study drug + 28 days].

The analysis of TEAEs will serve as primary endpoint of this trial.

If the start date and time of an AE are partially or completely missing, the AE will be assumed to be a TEAE if it cannot be definitely shown that the AE did not occur during the treatment emergent period

---

(worst case approach). Missing dates and times will not be replaced. The following approach will be followed:

- If the start time of an AE is missing but the start date is complete, an AE will only be excluded from TEAE if the start day is before the day of first study drug administration or the start date is after the end date of the treatment-emergent period
- If the start time and day are missing but the start month is complete, an AE will only be excluded from TEAE if the start month is before the month of first study drug administration or the start month is after the end month of the treatment-emergent period or if the stop date and time is before the start of first study drug administration
- If the start day and months are missing but the start year is complete, an AE will only be excluded from TEAE if the start year is before the year of first study drug administration or if the start year is after the end year of the treatment-emergent period or if the stop date and time is before the start of first study drug administration
- If the start date is completely missing, an AE will not be excluded from TEAE unless the stop date and time is before the start of first study drug administration

AEs starting during the study but before the first date of study drug administration will be classified as pre-treatment adverse events and will be presented in a separate adverse events listing.

An AE present prior to first study drug administration but increased in severity after treatment start, will also be included as TEAE.

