**12.12.1. Adverse Events**

All AEs which start after the first dose of trial medication until 28 days after last treatment will be considered as TEAEs. Adverse events that start during the trial but before the time of the first dose

of MOR202 (e.g. screening phase) will be classified as non-treatment emergent adverse events and will be presented in a separate AE listing.

Adverse events will be coded according to Medical Dictionary for Regulatory Activities (MedDRA), system organ class (SOC) and preferred term. Incidence and frequency of all AEs will be summarized by SOC, preferred term, relationship to treatment, severity and seriousness.

An AE summary table will be presented showing the number of events, number of subjects and the percentage of subjects in each cohort and overall having:

- All TEAEs
- TEAEs by maximum severity
- SAEs
- Drug-related TEAEs
- Drug-related TEAEs in each severity/toxicity grading
- TEAEs that led to treatment discontinuation
- IRRs by grade

Adverse events of special interest (AESI) in this trial are:

- Infusion related reactions to MOR202  $\geq$  grade 3
- Cytokine release syndrome
- Allergic reactions to MOR202
- Infections  $\geq$  grade 3
- Neutropenia  $\geq$  grade 3 ( $< 1.0 \times 10^9/L$ )
- Thrombocytopenia  $\geq$  grade 3 ( $< 50.0 \times 10^9/L$ )
- Major bleeds (defined as critical organ bleed or hemoglobin decrease of more than 20 g/L within 24 h)

The sponsor will describe AESI, in addition to those reported as SAEs. AESI tabulations will be analogous to the tabulation of TEAEs.

As part of one of the secondary endpoint, the sponsor will analyze the incidences and severity of AEs of MOR202 during the follow-up phase until EOS. Post-treatment AE tabulations will be analogous to the tabulation of TEAEs.

The sponsor will discuss other significant AEs as appropriate, e.g. laboratory abnormalities that qualify as AEs (other than those meeting the definition for serious) and any events that led to an intervention (including premature discontinuation of IMP, increase of dose interval, or significant additional concomitant therapy) in addition to those reported as SAEs.

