### **Post-Treatment Adverse Event**

Post-treatment AEs are defined as any adverse event reported within the following time interval (including the lower and upper limits), which is referred to as the post-treatment period:

[End date of study drug + 28 days + 1 day; Date of study discontinuation].

The analysis of post-treatment AEs will serve as one of the secondary endpoints.

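### The SAP's worsening rule for treatment-emergent AEs has no end date, so a screening-phase AE that first worsens in follow-up enters the primary endpoint; post-treatment AEs have no matching rule.

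*SAP*

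**What the plan says.** SAP 11.1 defines a closed treatment-emergent period, "Start date of study drug, End date of study drug + 28 days", with both ends included, and gives its role: "The analysis of TEAEs will serve as primary endpoint of this trial". Events with onset before dosing are set apart: "AEs starting during the study but before the first date of study drug administration will be classified as pre-treatment adverse events". One exception follows: "An AE present prior to first study drug administration but increased in severity after treatment start, will also be included as TEAE". It has a lower limit, treatment start, and no upper limit.

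For follow-up, the SAP says "Post-treatment AEs are defined as any adverse event reported within the following time interval", the interval being "End date of study drug + 28 days + 1 day; Date of study discontinuation". This is the basis of a secondary endpoint. It contains nothing on worsening. The listing rules in SAP 11.1.3 and 11.1.4 flag post-treatment AEs by their start. The table rules in SAP 11.1.3 show a repeated preferred term at its maximum toxicity grade, without requiring that the grade was reached in the period being tabulated.

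Protocol 12.12.1 decides by start date alone, closes at 28 days after last treatment and has no worsening rule. Its wording for events that start before first dose is "e.g. screening phase) will be classified as non-treatment emergent adverse events". Protocol 3.2 gives the same 28-day window.

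Protocol 10.8.10 collects AEs from consent to the end-of-study visit (EOS), so late worsening will be observed. Protocol 10.8.5 allows a clinically significant deterioration after consent to be an AE in its own right. Neither document says whether a grade increase in an ongoing AE opens a new record.

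**The concern.** The worsening clause alone decides whether an AE with onset before dosing enters the primary endpoint, and a programmer would implement it as written. A first worsening months after the last dose would then count as treatment-emergent, in a trial that separates on-treatment safety (primary) from follow-up safety (secondary).

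The missing counterpart raises a second question: in which period, and at what grade, is an on-treatment AE shown when it worsens in follow-up? What is at stake is the allocation of events and maximum grades between two endpoints.

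**Working it through.** **1. The plan's own AE figures (Protocol 12.5, SAP 6.3).** The chance of seeing at least one event is 1 − (1 − p)^n.
- Cohort 1: 1 − 0.90^20 = 0.878, stated as 88%.
- Cohort 2: 1 − 0.85^10 = 0.803, stated as 80%.

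Both reproduce, and neither depends on the point raised here.

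**2. How far the uncapped clause reaches.** Inputs are the nominal days in Protocol Table 2: last dose (C6D1) Day 141, EOS Day 366 ± 14 days.
- End of the TEAE window: 141 + 28 = Day 169.
- Nominal time from window end to EOS: 366 − 169 = 197 days.
- Range with the visit window: 352 − 169 = 183 to 380 − 169 = 211 days, about 6 to 7 months.
- A worsening on Day 300 is 300 − 169 = 131 days past the window.

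**3. Classification of three cases.** Because the recording rule is not stated, each case is taken both ways: the worsening stays on the original record, or it opens a new record with its own start date.

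| Case | Recording | SAP as written | Clause capped, post-treatment rule added |
|---|---|---|---|
| Screening onset, worsens Day 100 | either | TEAE | TEAE |
| Screening onset, first worsens Day 300 | one record | TEAE | post-treatment |
| Screening onset, first worsens Day 300 | new record | TEAE and post-treatment | post-treatment |
| Onset Day 100, worsens Day 300 | one record | TEAE only | TEAE and post-treatment |
| Onset Day 100, worsens Day 300 | new record | TEAE and post-treatment | TEAE and post-treatment |

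The Day 300 screening case is a TEAE under either recording, because the clause describes an event that was present before dosing and increased afterwards. With separate records, a program would have to link the two to apply the clause. Protocol 12.12.1 never makes this case a TEAE: with one record it is non-treatment-emergent, and with a new record it starts on Day 300, outside the window.

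The Day 100 onset case depends on the recording. With one record it is absent from the post-treatment tables, and its Day 300 grade becomes the maximum grade in the TEAE tables. With a new record it is already in both periods.

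**4. Weight of one subject.** 1/20 = 5 points in Cohort 1, 1/10 = 10 points in Cohort 2, 1/30 = 3.3 points overall.

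**The case against.** The strongest reply is that the clause sits in the paragraph that closes the treatment-emergent period, so worsening within that period was probably meant. That is plausible, but the text does not say it.

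The case is also narrow. The AE must begin within a screening phase of at most 42 days (Protocol 10.1), still be ongoing after about Day 169, and first worsen only then; one that also worsened on treatment is a TEAE under either wording. Subjects who withdraw or start prohibited immunosuppression during treatment do not enter follow-up (Protocol 8.8.4, 8.8.5). This stands, and it limits the size.

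A reader might infer that an on-treatment AE that worsens in follow-up is always missing from the follow-up endpoint, so that late deterioration is understated. The documents do not support that. Protocol 10.8.5 can be read as making the worsening a new AE, which would then start in follow-up. The SAP's post-treatment definition also refers to events reported, not started, in the interval, although its listing flags use start dates. Even with one record the event is not lost: it stays in the TEAE tables at its maximum grade, which raises the primary-endpoint severity. In the other direction, if every worsening opened a new record, the SAP's clause would be largely redundant for worsening inside the window, which hints at one record per AE. That is an inference, and it does not settle the matter.

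A reader might also take 197 of 366 days (54%) to mean that about half of such worsenings are misplaced. That is a share of calendar time. It would be a share of events only if every screening AE stayed open to EOS with a constant daily chance of worsening, and nothing in the documents supports this.

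Finally, Protocol 12.7 leaves analysis detail to the SAP. It also requires deviations from the protocol's outlined analysis to be described in the trial report, so the difference still has to be reported.

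**Conclusion.** The point holds for the missing upper limit. As written, SAP 11.1 places a screening-phase AE that first worsens in follow-up in the primary endpoint, contrary to its own closed interval and to Protocol 12.12.1. This needs no assumption beyond a literal reading.

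The missing post-treatment counterpart is a conditional problem. It matters if a worsening stays on the original AE record, and it makes no difference to an on-treatment AE if a new record is opened.

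The effect is the allocation of probably few events, and of their maximum grades, between two descriptive endpoints. The documents give no rate for such worsening, so no expected count can be stated; one subject is worth 5 points in Cohort 1 and 10 in Cohort 2. Sample size is unaffected, and no hypothesis test is planned. The change is worth making because it concerns the primary endpoint and costs little.

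**What to change.** Amend SAP 11.1 as follows.
- Limit the clause to an AE present before first dose that *increased in severity on or after first dose and up to end date of study drug + 28 days*.
- Count an AE that worsens after that date as a post-treatment AE at the increased grade, while the TEAE tables keep the maximum grade reached within the window.
- Apply both rules using the start date of the worsening record or the date of the grade change, whichever the eCRF holds, and state which it is.
- Describe the difference from the start-date rule of Protocol 12.12.1 in the clinical study report, as Protocol 12.7 requires.

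The cost is a few sentences and minor programming. The AE data items named in SAP 11.1 do not include a grade-change date, so its availability must be checked; the existing clause already needs some way to date or recognise a worsening. One AE may then appear in both periods at different grades, which a table footnote should explain.
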